1.2. Study Design

Overview of Stu	dy Design and Key Features		
	Week 0 2 4 8 12 16 20 24 26 28 32 36 40 44 48 52		
	Visit 2 3 4 5 6 7 8 9 10 11 12 13 14 15 16 17		
	SoC** + GSK3511294 100 mg SC N=250 planned		
Pre-Screen V0	Screening V1/ Run-in Screening V1/ Run-in Screening V1/ Run-in R* 2:1 Screening V1/ R* 1st Dose IP Composition Composition Composition Composition Composition Composition Composition Composition Composition Composition Composition Composition Composition Composition Composition Composition Composition Composition Composition Composition Composition Composition Composition Composition Composition Composition Composition Composition Composition Composition Composition Composition Composition Composition Composition Composition Composition Composition Composition Composition Composition Composition Composition Composition Composition Composition Composition Composition Composition Composition Composition Composition Composition Composition Composition Composition Composition Composition Composition Composition Composition Composition Composition Composition Composition Composition Composition Composition Composition Composition Composition Composition Composition Composition Composition Composition Composition Composition Composition Composition Composition Composition Composition Composition Composition Composition Composition Composition Composition Composition Composition Composition Composition Composition Composition Composition Composition Composition Composition Composition Composition Composition Composition Composition Composition Composition Composition Composition Composition Composition Composition Composition Composition Composition Composition Composition Composition Composition Composition Composition Composition Composition Composition Composition Composition Composition Composition Composition Composition Composition Composition Composition Composition Composition Composition Composition Composition Composition Composition Composition Composition Composition Composition Composition Composition Composition Composition Composition Composition Co		
	SoC** + Placebo N=125 planned		
Pre-Screening	Screening V1/ V0 Run-in Period Study Intervention Period		
0 to 2 weeks	≥1 week (max 6 weeks) 52 Weeks (Last dose at Week 26)		
of ≥150 cells/µL at S be randomised 2:1 to ** SoC = medium to	n: To be randomised participants without a historical blood eosinophil count of ≥300 cells/µL must have a blood eosinophil count icreening Visit 1. Participants will remain on their standard of care (SoC) asthma therapy throughout the intervention period and o receive GSK3511294 (100 mg) or placebo. high dose ICS (≥440 µg FP HFA daily or clinical comparability) plus additional controller. SoC asthma therapy to exclude biologic extension. Willing participants will continue directly into OLE Study 212895. Participants unwilling to continue will have a follow- e Exit Visit.		
Design	Phase 3A		
Features	52-week treatment period		
	Randomised		
	Double-blind		
	Placebo-controlled		
	Parallel group		
	Multi-centre		
	Approximately 540 participants with severe uncontrolled asthma with an eosinophilic		
	phenotype will be screened to ensure the randomisation of 375 participants in a 2:1		
	ratio to GSK3511294 (n=250) and matching placebo (n=125).		
	 A sample size of 375 randomised will provide 99% power to demonstrate superiority of GSK3511294 100 mg SC + SoC following two doses (at Week 0 and at Week 26) 		
	compared with placebo + SoC in annualised rate of clinically significant exacerbations		
	over 52 weeks, based on the true annualised rate of exacerbations in the placebo arm		
	being 1.18 , an assumed true treatment difference of a 50% reduction and at a 5%		
	two-sided significance level.		
	 Participants who receive both doses of study intervention and complete the Exit Visit will be eligible to participate in an open-label extension (OLE) study (Study 212895), during which they will receive two doses of open-label GSK3511294 100 mg SC over another 52 weeks. 		
Study	The study will consist of a pre-screen period (0-2 weeks), a run-in period (1-6 weeks), and a		
intervention	study intervention period (52 weeks). After the run-in period, participants will be randomised in a		
and Study	2:1 ratio using an interactive response technology (IRT) system in a blinded manner to receive		
intervention	either GSK3511294 100 mg or placebo by SC injection. Randomisation will be stratified based		
Assignment	on baseline ICS dose (medium or high dose). Two doses of study intervention will be		
-	administered in the clinic: the first at randomisation Visit 2 (Week 0) and the second at Visit 10		
	(Week 26). Participants will be assessed at each scheduled visit (a total of 17 study visits)		
	during the 52-week treatment phase. Study visits may be conducted remotely (by a home		
	healthcare professional) or virtually, however, in-person clinic visits are required for the		
	following: pre-screening Visit 0, screening Visit 1, randomisation Visit 2, Visit 3, Visit 10, Visit 11,		
	Exit Visit 17, and WS Visit (if applicable).		
	Destination of the second second devices of the second s		
	Participants will remain on their existing stable maintenance asthma therapy throughout the		
Intorim	study.		
Interim Analysis			

2. STATISTICAL HYPOTHESES

The primary study objective is to test for the superiority of GSK3511294 100 mg SC + SoC following two doses (at Week 0 and at Week 26) compared with placebo + SoC, assessed by the annualised rate of clinically significant exacerbations measured over the study intervention period of 52 weeks.

The study will test at a 5% two-sided significance level the null hypothesis that there is no difference in annualised exacerbation rate between GSK3511294 and placebo.

2.1. Multiplicity Adjustment

The treatment comparison of interest for the primary and secondary endpoints is GSK3511294 100 mg SC + SoC vs placebo + SoC. A fixed sequence hierarchical testing procedure will be used to provide strong control of Type I error for multiplicity arising from the primary and multiple secondary endpoints. This will be carried out using a stepdown closed testing procedure where inference for an endpoint in the predefined hierarchy will be dependent on statistical significance having been achieved for the previous endpoints in the hierarchy. For example, for the primary endpoint, GSK3511294 + SoC will be compared to placebo + SoC at a two-sided 5% level. The next endpoint in the hierarchy (i.e. the first secondary endpoint) will be tested only if the test for the primary endpoint is significant at the two-sided 5% level. Testing will continue down the hierarchy for the remaining endpoints in an equivalent manner only if the previous endpoint in the hierarchy achieves statistical significance.

The hierarchy of the primary and secondary endpoints to be tested is as follows:

- 1. Annualised rate of clinically significant exacerbations over 52 weeks
- 2. Change from baseline in SGRQ at Week 52
- 3. Change from baseline in ACQ-5 at Week 52
- 4. Change from baseline in clinic pre-bronchodilator FEV_1 at Week 52
- 5. Change from baseline in ANSD at Week 52
- 6. Change from baseline in ADSD at Week 52
- 7. Annualised rate of exacerbations requiring hospitalisation and/or ED visit over 52 weeks

3. ANALYSIS SETS

Analysis Set	Definition / Criteria	Analyses Evaluated
Screened	All participants who sign the ICF (not including subjects who	 Study Population
	failed at pre-screening).	
Enrolled	All participants who entered the study. Note screening failures (who never passed screening even if rescreened) and participants screened but never enrolled into the study (Met eligibility but not needed) are excluded from the Enrolled analysis set as they did not enter the study.	 Study Population
Randomised	All participants who were randomly assigned to study	 Study Population

Analysis Set	Definition / Criteria	Α	nalyses Evaluated
	intervention in the study.		
Full Analysis Set (FAS)	All randomised participants who receive at least one dose of study intervention excluding participants from sites 250085 & 250523. Data will be analysed according to randomised treatment arm.	• • • •	Study Population Efficacy Immunogenicity PD
FAS-PROMIS	All participants in the FAS population for whom at least one PROMIS fatigue items were administered	•	Health Resource Use Efficacy (PROMIS)
FAS- ADSD/ANSD	All participants in the FAS population for whom at least one ADSD/ANSD questionnaire were administered	•	Efficacy (ADSD/ANSD)
FAS-Japan	All participants in the FAS population who are enrolled from Japan and with Japanese heritage only	•	Study Population Efficacy PD
FAS-Non-Japan	All participants in the FAS population who are not in FAS-Japan analysis set	•	PD
Safety	All randomised participants who receive at least one dose of study intervention excluding participants from sites 250085 & 250523. Participants will be analysed according to the intervention they are allocated at randomisation, unless a participant receives a different intervention to the randomised intervention at all protocol-defined administrations at which study medication was received, in which case the participant will be analysed according to the actual intervention they received. This population will serve as the primary population for analyses of safety endpoints.	•	Safety
Safety-Japan	All participants in the Safety population who are enrolled from Japan and with Japanese heritage only	•	Safety
Safety-Non- Japan	All participants in the Safety population who are not in Safety- Japan analysis set	•	Not planned in this SAP but flagged for future analysis
PK	All participants in the FAS population for whom at least one pharmacokinetic sample was obtained, analysed and was measurable.	•	PK
PK-Japan	All participants in the PK population who are enrolled from Japan and with Japanese heritage only	•	РК
PK-Non-Japan	All participants in the PK population who are not in PK- Japan analysis set	•	РК
FAS-Modified	All participants in the FAS population plus randomised particiants from sites 250085 & 250523 who receive at least one dose of study intervention.	•	Efficacy (Primary and Secondary)
Safety-Modified	All participants in the Safety population plus randomised particiants from sites 250085 & 250523 who received at least one dose of study intervention. Participants will be analysed according to the intervention they are allocated at randomisation, unless a participant receives a different intervention to the randomised intervention at all protocol- defined administrations at which study medication was received, in which case the participant will be analysed according to the actual intervention they received.	•	Key Safety
FAS- ADSD/ANSD- Modified	All participants in the FAS-ADSD/ANSD population plus randomised participants from sites 250085 & 250523 who receive at least one dose of study intervention.	•	Efficacy (ADSD/ANSD)

Note: GCP non-compliance/significant data integrity concern at Sites 250085 & 250523 was identified.

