6.8. Treatment of Overdose

The dose of GSK3511294 that is considered to be an overdose has not been defined. There are no known antidotes and there is no specific treatment for a suspected overdose. In FTIH study 205722 (refer to the current IB [GlaxoSmithKline Document Number [2016N295843_03](#) or later]), single SC doses of GSK3511294 up to 300 mg were well tolerated by adult participants with mild/moderate asthma (6 participants received a 300 mg SC dose).

Each PFS will enable the delivery of a single dose of study intervention (see Section 6.1). In the event of an overdose, the investigator should:

- Contact the Medical Monitor immediately.
- Treat the participant with active supportive care as dictated by the participant's clinical status in the knowledge of the long half-life (approximately 41 days) of GSK3511294.
- Closely monitor the participant for AE/SAE and laboratory abnormalities for 30 weeks following the last administered dose.
- Document the quantity of the excess dose as well as the duration of the overdosing in the CRF.

Decisions regarding discontinuation or delay of another dose of study intervention will be made by the investigator in consultation with the Medical Monitor based on the clinical evaluation of the participant.

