9.3. Analysis Sets

For the purpose of analyses, the following populations are defined:

Population	Description
Screened	All participants who sign the ICF.
Enrolled	All participants who entered the study. Note screening failures (who never passed screening even if rescreened) and participants screened but never enrolled into the study (Met eligibility but not needed) are excluded from the Enrolled analysis set as they did not enter the study.

Randomised	All participants who were randomly assigned to study intervention in the study.
Full Analysis Set (FAS)	All randomised participants who receive at least one dose of study intervention. Participants will be analysed according to the intervention they are allocated at randomisation. This population will serve as the primary population for analyses of efficacy endpoints.
Safety	All randomised participants who receive at least one dose of study intervention. Participants will be analysed according to the intervention they are allocated at randomisation, unless a participant receives a different intervention to the randomised intervention at all protocol-defined administrations, in which case the participant will be analysed according to the actual intervention they received. This population will serve as the primary population for analyses of safety endpoints.

Further populations to be used for other assessments will be defined in the statistical analysis plan (SAP).

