4.6.1. Extent of Exposure

Two doses of study treatment will be administered during study treatment period: the first at randomisation Visit 2 (Week 0) and the second at Visit 10 (Week 26). Each dose is viewed as providing therapeutic coverage for 26 weeks (182 days). The number of treatments administered and the number of days exposure will be summarised descriptively and listed. Total subject-year exposure will also be presented.

Number of days of exposure to study treatment will be calculated as follow:

Duration of Exposure in Days = (Date of Final Dose) – (Date of First Dose) + 182

Subject years exposure is calculated as follow:

Subject Years Exposure = ((Date of Final Dose) – (Date of First Dose) + 182)/365.25

The exposure summary will also be presented by age subgroup $(12-17, 18-64, \ge 65)$.

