4.6.2.1. Adverse Events of Special Interest

Adverse events of special interest (AESI) for GSK3511294 program include:

• Allergic (Type 1 hypersensitivity) reactions including anaphylaxis

Note: these events will be assessed by the investigator as to whether they meet the diagnostic criteria for anaphylaxis as outlined by the 2006 Joint NIAID/FAAN Second Symposium on Anaphylaxis.

- Type III hypersensitivity (immune complex disease/vasculitis) reactions
- Local injection site reactions
- QTc prolongation

AESI reported by the investigator as systemic reactions (further categorised by the investigator as either allergic [type I hypersensitivity] or other systemic reactions and assessed against Sampson criteria for anaphylaxis) are collected via targeted eCRF within the study. Vasculitis events and local injection site reactions are also collected via targeted eCRF within the study.

Separate summary tables showing the number and percent of subjects with each type of AESI (excluding QTc prolongation) broken down by preferred term will be created.

For each type of AESI (excluding QTc prolongation) a profile summary table will be produced containing information including, but not limited to, the number of occurrences of the event, event characteristics, time to onset, intensity, outcome and action taken.

A summary of the incidence of serious adverse events and adverse events of special interest (excluding QTc prolongation) will be produced displaying the relative risk and risk difference and their 95% CIs between and GSK3511294 and placebo.

AESI of QTc prolongation will be summarised as detailed in Section 4.6.3.3 ECG.

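### A placebo participant given one active and one placebo dose stays in the placebo group for safety, so a reaction to the active dose counts against placebo

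*SAP*

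**What the plan says.** For the Safety set, SAP Section 3 starts from the randomised arm: "Participants will be analysed according to the intervention they are allocated at randomisation". The only exception applies "unless a participant receives a different intervention to the randomised intervention at all protocol-defined administrations at which study medication was received"; that participant is then analysed by what was actually received. The Safety-Modified set, which adds back the two excluded sites, repeats the rule.

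Protocol 9.3 has the same exception without the closing qualifier: "unless a participant receives a different intervention to the randomised intervention at all protocol-defined administrations, in which case the participant will be analysed" by actual treatment.

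Two doses are planned, at Week 0 and Week 26. SAP 4.6.1 credits each with 182 days of coverage. Protocol 6.8 refers to the "long half-life (approximately 41 days) of GSK3511294".

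SAP 4.6 puts all safety analyses on the Safety set unless otherwise specified. SAP 4.6.2.1 plans a summary of serious adverse events and adverse events of special interest "displaying the relative risk and risk difference and their 95% CIs", leaving out QTc prolongation, which goes to the ECG summaries in SAP 4.6.3.3.

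**The concern.** When only two doses are given, a rule that reassigns a participant only if every dose was wrong takes no account of one wrong dose out of two. By the plan's own accounting, one active dose is half of the planned exposure: 182 of 364 days. A placebo participant with that exposure contributes to the comparator arm in every Safety-set output, including the exposure-adjusted incidence rates of SAP 4.6.2.

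What is at stake is the comparison of uncommon reactions. The placebo arm is half the size of the active arm, so one drug-caused event placed there weighs twice as much as one in the active arm. It also pulls the estimated difference towards making the drug look safer. Safety-Modified offers no alternative view, because it uses the same rule.

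**Working it through.** **Inputs**
- Allocation rules: SAP Section 3 and Protocol 9.3.
- Two administrations, 182 days of coverage each: SAP 4.6.1.
- Planned arms 250 and 125: SAP Section 5. The Safety set excludes two sites, so actual denominators may be somewhat smaller.
- Number of misdosed participants: not in the documents. Assumed 1 to 3 for illustration only.

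The plan states no figure on this point, so there is none to reproduce.

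**Step 1. Apply each rule to every relevant dose sequence**

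| Randomised to | Received Week 0 / Week 26 | SAP Section 3 | Protocol 9.3, read literally | Any active dose counts as active |
|---|---|---|---|---|
| Placebo | active / placebo | placebo | placebo | active |
| Placebo | placebo / active | placebo | placebo | active |
| Placebo | active / active | active | active | active |
| Placebo | active / none | active | placebo | active |
| GSK3511294 | active / placebo | active | active | active |
| GSK3511294 | placebo / active | active | active | active |
| GSK3511294 | placebo / placebo | placebo | placebo | placebo |
| GSK3511294 | placebo / none | placebo | active | placebo |

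The SAP rule and an any-active rule differ only in the first two rows. The SAP and the literal protocol rule differ in the two single-dose rows.

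**Step 2. Which sequences can carry which events**

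Protocol 7.1 bars a further dose after severe allergic reaction or anaphylaxis without clear alternative cause, after confirmed or unexplained suspected vasculitis, and after QTc stopping criteria are met. If a wrong Week 0 dose causes one of these, the participant normally falls in the active / none row, which the SAP already handles. The gap that remains is (a) a wrong Week 26 dose after a correct placebo dose, for any reaction, and (b) a wrong Week 0 dose followed by placebo, for reactions that do not stop dosing or that begin after the second dose.

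**Step 3. Size per case**

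One misplaced case changes the placebo proportion by 1/125 = 0.8 percentage points.

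Suppose the trial's only anaphylaxis follows a wrong Week 26 dose in a placebo participant:
- SAP rule: 0/250 − 1/125 = −0.8 points.
- Any-active rule: 1/251 − 0/124 = +0.4 points.

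Simple Wald 95% intervals are about −2.4 to +0.8 and −0.4 to +1.2 points. Both include zero.

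**Step 4. A less extreme illustration**

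Assume 5/250 active and 1/125 placebo events, plus *m* mixed-dose placebo participants who each react to the active dose. The SAP risk difference is 5/250 − (1+*m*)/125. The any-active difference is (5+*m*)/(250+*m*) − 1/(125−*m*).

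| *m* | SAP rule | Any-active rule |
|---|---|---|
| 0 | +1.20 points | +1.20 points |
| 1 | 2.00% − 1.60% = +0.40 points | 2.39% − 0.81% = +1.58 points |
| 2 | 2.00% − 2.40% = −0.40 points | 2.78% − 0.81% = +1.96 points |
| 3 | 2.00% − 3.20% = −1.20 points | 3.16% − 0.82% = +2.34 points |

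With *m* = 0 the rules agree.

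**The case against.** The strongest reply is that this is unlikely to matter. Each participant gets two doses, in clinic, under supervision, with IRT assignment. A distortion needs a dosing error and then a reaction in the same person. The documents report no misdosing, and the contrast in Step 3 is between two inconclusive estimates. This stands, and it is why the point is minor.

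Three stronger readings are tempting, and the documents do not support them.

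- *Any placebo participant given an active dose is counted as placebo.* No. The SAP tests only administrations at which medication was received, so a participant whose single dose was active is moved to active. That covers most dose-stopping reactions to a wrong Week 0 dose.
- *One misplaced QTc case could reverse a planned risk difference.* No. SAP 4.6.2.1 excludes QTc prolongation from that table. It is affected only through the summaries by treatment in SAP 4.6.3.3.
- *The rule always favours the drug.* No. That holds for adverse reactions caused by the active dose. Events before a wrong Week 26 dose are true placebo events and are correctly placed. Exacerbations meeting the serious adverse event definition are also recorded as such (Protocol 8.2.2). If the erroneous dose prevents one, keeping that person in placebo lowers the placebo rate and works against the drug.

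The any-active rule has a bias of its own: it can move up to 26 weeks of placebo-period events into the active arm. It is also fair to say that SAP 4.6.1 lists treatments administered and exposure, that the special-interest profiles give time to onset, and that the Output and Programming Specification, which is not among the documents, may add displays. Those would help a reader find a mixed-dose case. They would not change the arm in which the SAP counts it.

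**Conclusion.** The concern holds in a narrow form. Under SAP Section 3, a placebo participant with one active and one placebo dose is analysed as placebo in both safety sets, and an adverse reaction caused by the active dose is counted in the comparator arm. The available documents contain no correcting rule, attribution by preceding dose or sensitivity display for such participants.

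The size is about 0.8 percentage points on the placebo rate per misplaced case, taking the planned 125 as denominator. Everything beyond that rests on assumed counts. If no mixed dosing occurs, no result changes.

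Separately, the SAP and Protocol 9.3 give different answers for a participant who received only one dose, of the wrong treatment. SAP 4.12 does not record that difference. Severity: minor; a cheap improvement best settled before unblinding, since a later change would look driven by results.

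**What to change.** In SAP Section 3, for Safety and Safety-Modified, replace the exception with a rule that any participant who received at least one dose of GSK3511294 is analysed in the GSK3511294 group, and all other treated participants as placebo.

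Add a listing of mixed-dose participants with both dose dates, treatment received at each, and event onset dates, so that events before the active dose are visible as placebo-period events.

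Align Protocol 9.3 with the new wording, which also removes the single-dose discrepancy, and enter the change in SAP 4.12. State in SAP 4.9 which assignment the adverse event panel of the risk-benefit plot follows: that section names the Full Analysis Set, which is by randomised arm, but takes its adverse event results from SAP 4.6.2.1.

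The cost is a sentence in two SAP definitions, one listing, the protocol alignment and the SAP 4.12 entry. The statistical downside is that events before an erroneous active dose are also counted as active. This is the conservative direction for safety, and the listing makes it visible.
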